A13	
Criterion modified per Amendment 1
 
A13.1 Participants must have serum HBsAg >5 IU/mL at screening, as assessed by quantitative HBsAg assay.

A14	
Participants must have:
 
 a. Fibroscan liver stiffness measurement \leq9.0 kPa within 6 months prior to screening or at the time of screening, OR b. If a Fibroscan result is not available: a liver biopsy result classified as Metavir F0-F2 within 1 year prior to screening. 
Note: Other radiologic liver staging modalities (eg, acoustic radiation force impulse) might be used if standard practice at the site or if otherwise validated and agreed with the Sponsor. Results should be equivalent to Metavir F0-F2.
 
Note: Conventional imaging procedures (eg, conventional liver ultrasound, computed tomography [CT] or magnetic resonance imaging [MRI]) and serum marker panels are not allowed to rule out severe fibrosis or cirrhosis.

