## 1. INTRODUCTION

The statistical analysis plan (SAP) for the 73763989PAHPB2007 phase 2 describes the statistical analyses, and definitions to assess the efficacy, safety, tolerability, and PK of the combination of JNJ-73763989 (JNJ-3989), nucleos(t)ide analogs (NAs), and pegylated interferon-alpha2a (PegIFN- $\alpha$ 2a) in long-term ( $\geq 2$  years of NA treatment) virologically suppressed, HBeAg-negative, chronic HBV-infected (CHB), adult participants.

This study is part of the platform trial PLATFORMMPAHPB2001 in participants with CHB. The protocol for 73763989PAHPB2007 constitutes the Intervention Specific Appendix that describes all the specific and/or additional features of this study complementing the common design elements of the platform trial described in the Master Protocol.

This SAP is to be interpreted in conjunction with the clinical protocol amendment 1 finalized on 6 October 2021, and with the Master Protocol Amendment-3 for PLATFORMPAHPB2001 finalized on 21 January 2021.

Details on pharmacokinetic (PK) and pharmacokinetic/pharmacodynamic (PK/PD) analyses will be described in a separate analysis and modelling plan.

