Safety	All participants who received at least 1 dose of study intervention within this ISA. Participants will be analyzed according to the study intervention they actually received.
Per Protocol Analysis Set (PP)	All participants in the FAS who do not have any of the selected major protocol deviations that may affect the assessment of efficacy in terms of the primary endpoint at Week 24. The selected major protocol deviations for efficacy analysis purposes that will be used to identify the participants included in the PP set are described in Section 6.4. Participants will be analyzed according to the study intervention they were randomly assigned to.
Pharmacokinetics Analysis Set	All participants who received at least 1 dose of study intervention and have at least 1 valid blood sample drawn for PK analysis.

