#### 6.4. Appendix 4 Protocol Deviations

In general, the following list of major protocol deviations may have the potential to impact participants' rights, safety or well-being, or the integrity and/or result of the clinical study. Participants with major protocol deviations will be identified prior to database lock and the participants with major protocol deviations will be summarized by category.

- Developed withdrawal criteria but not withdrawn
- Entered but did not satisfy criteria
- Received a disallowed concomitant treatment
- Received wrong treatment or incorrect dose
- Other

All major protocol deviations will be tabulated by coded term for the FAS. A listing of the major protocol deviations will be also presented.

A subset of major protocol deviations that may affect the assessment of efficacy (Table 13) will be identified and finalized prior to database lock. The major deviations that are selected to exclude participants for the PP set are listed at Table 13. The flag for Intercurrent Event is added to each deviation for facilitating the implementation of the estimands for the primary endpoint.

The count and proportion of FAS participants without any major protocol deviations will be summarized by intervention arm, accompanied by count and proportion of FAS participants who had a major protocol deviation with the incidence of the major protocol deviations.

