9	In the investigator's opinion, the participant is able to understand and comply with protocol requirements, instructions, and study restrictions and is likely to complete the study as planned per ISA (including the procedures outlined in the Master Protocol PLATFORMPAHPB2001)	Inclusion criteria M09 not met  In the investigator's opinion, the participant is able to understand and comply with protocol requirements, instructions, and study restrictions and is likely to complete the study as planned per ISA (including the procedures outlined in the Master Protocol PLATFORMPAHPB2001)	Entered but did not satisfy criteria	Yes	No
10	Male participants must agree to wear a condom when engaging in any activity that allows for passage of ejaculate to another person during the study intervention period and until 90 days after last dose of study intervention	Inclusion criteria A10(adapted from M10) not met  Male participants must agree to wear a condom when engaging in any activity that allows for passage of ejaculate to another person during the study	Entered but did not satisfy criteria	Yes	No

		intervention period and until 90 days after last dose of study intervention			
11	Female participants must agree not to donate eggs (ova, oocytes) for the purposes of assisted reproduction during the study intervention period and until 90 days after last dose of study intervention	Inclusion criteria A11 not met  Female participants must agree not to donate eggs (ova, oocytes) for the purposes of assisted reproduction during the study intervention period and until 90 days after last dose of study intervention	Entered but did not satisfy criteria	Yes	No
12	Male participants must agree not to donate sperm for the purpose of reproduction during the study intervention period and until 90 days after last dose of study intervention	Inclusion criteria A12 not met  Male participants must agree not to donate sperm for the purpose of reproduction during the study intervention period and until 90 days after last dose of study intervention	Entered but did not satisfy criteria	Yes	No
13	Participants must have serum HBsAg >100 IU/mL at screening, as assessed by quantitative HBsAg assay	Inclusion criteria A13 not met  Participants must have serum HBsAg >100 IU/mL at screening, as assessed by quantitative HBsAg assay	Entered but did not satisfy criteria	Yes	No

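### SAP Table 13, row 13 keeps the superseded HBsAg entry limit of >100 IU/mL, so participants validly enrolled under Amendment 1 with HBsAg above 5 and up to 100 IU/mL would be listed as major deviators and dropped from the per-protocol set

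*SAP*

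**What the plan says.** Protocol section 5.1 marks criterion A13 as modified by Amendment 1 and now reads "A13.1 Participants must have serum HBsAg >5 IU/mL at screening, as assessed by quantitative HBsAg assay". The amendment summary gives the previous limit as 100 IU/mL and says the primary endpoint was adjusted to accommodate the change.

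The SAP ties itself to that version: "This SAP is to be interpreted in conjunction with the clinical protocol amendment 1 finalized on 6 October 2021". Its Appendix 2 declares no changes to the protocol-planned analyses.

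SAP Appendix 4 (section 6.4), Table 13, row 13 nevertheless states A13 as "Participants must have serum HBsAg >100 IU/mL at screening, as assessed by quantitative HBsAg assay", in both the description column and the deviation-term column. The row is coded "Entered but did not satisfy criteria", with exclusion from PP set to Yes and intercurrent event set to No.

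Table 2 defines the PP set, for the Week 24 primary endpoint, as "All participants in the FAS who do not have any of the selected major protocol deviations that may affect the assessment of efficacy". Appendix 4 supplies the link: "The major deviations that are selected to exclude participants for the PP set are listed at Table 13".

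**The concern.** The SAP and the protocol it implements give different limits for the same inclusion criterion, and the SAP uses its limit to define an analysis set. Following the SAP literally would have two effects.

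- **PP analysis.** The supplementary estimand of the primary endpoint (SAP 5.3.3) would leave out the participants whom the amendment made eligible. That estimand covers both the test against 2% and the between-arm comparisons. It would become partly a restriction on baseline HBsAg, which is itself a randomization stratification factor (cut at 1,000 IU/mL). A difference between FAS and PP results could no longer be read as the effect of protocol adherence.
- **Deviation reporting.** The major-deviation tables and listing (Appendix 4), and the summary of PP exclusions by arm and deviation type (SAP 5.3.3.1.2), would show compliant enrolment as eligibility breaches.

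**Working it through.** **1. The two limits compared**

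| | Protocol 5.1, A13.1 | SAP Table 13, row 13 |
|---|---|---|
| Screening HBsAg required | >5 IU/mL | >100 IU/mL |
| Screening value of 50 IU/mL | eligible | A13 deviation |
| PP set | no exclusion on this ground | excluded, no qualifier |

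The affected group is screening HBsAg above 5 and up to 100 IU/mL.

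**2. Does the table leave room for discretion?** Rows 33 to 50 and 62 to 67 make PP exclusion depend on case-by-case review, and row 30 restricts its Yes to two situations. Row 13 has neither qualifier.

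**3. Do the documents expect such participants?** Yes. Protocol 9.4.2.3 discusses the virtual control for participants with screening HBsAg of 100 IU/mL or less. SAP Table 8 has a baseline subgroup below 100 IU/mL, and Table 12 has a matching category. The SAP tables use baseline rather than screening values, so they describe a closely related group, not an identical one.

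**4. The plan's own figures.** These are not in dispute and are reproduced only as a reference.
- Primary test: exact binomial, n = 30, 2% against 32%. At one-sided 0.05/3, rejection needs at least 4 of 30 responders and power is 99.5%, consistent with the stated >95%.
- Pairwise: 80% against 50%, n = 30 per arm, Hochberg at one-sided 0.05. Simulated power per true difference is 0.67 to 0.68, matching the stated 68%.
- Size: 30 / (1 − 0.10) = 33.3, rounded up to 34 per arm; 3 × 34 = 102.

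**5. Number removed.** The affected share f is not in the documents, so a range is assumed.

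| Assumed f | Of 102 (102f) | Per arm of 34 (34f) | n per arm left from 30, 30(1 − f) |
|---|---|---|---|
| 10% | 10 | 3 | 27 |
| 20% | 20 | 7 | 24 |
| 30% | 31 | 10 | 21 |

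**6. Shift in the PP rate.** Let r_L be the response rate in the affected group and r_H the rate in the rest. Considering row 13 alone:

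- FAS rate = f·r_L + (1 − f)·r_H
- PP rate = r_H
- PP − FAS = f·(r_H − r_L)

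For an assumed absolute difference of 20 points, the shift is 0.10 × 20 = 2, 0.20 × 20 = 4 or 0.30 × 20 = 6 points. The direction depends on which group responds better, which the documents do not say. A difference is plausible: a 2 log10 fall from 100 IU/mL ends at 1 IU/mL, whereas from 5 IU/mL it ends at 0.05 IU/mL, the assay LLOQ in SAP Table 5.

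**7. Power within the PP set.** Pairwise power by a two-proportion formula at one-sided 0.025 is 0.69 at n = 30 and falls to 0.64, 0.59 and 0.53 at n = 27, 24 and 21. Primary-test power in the PP set stays high: 98.3% at n = 21, and 95.8% at n = 18 (40% removed).

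**The case against.** The strongest reply is that the harm is neither certain nor central. Table 13 classifies deviations entered in an issue system; nothing in the SAP derives an A13 breach by program from the screening value. A participant who meets A13.1 has met the protocol's criterion, so a site or monitor may never log a deviation. The efficacy-relevant subset "will be identified and finalized prior to database lock", which gives a further chance to notice the stale text. The main analysis uses the FAS and row 13 is not an intercurrent event, so the primary tests, the Hochberg procedure and their power are unchanged. The SAP itself acknowledges that the PP analysis is biased and requires exclusions to be tabulated by type, so a cluster of A13 exclusions would be visible. Other rows also drive PP exclusion, so a gap between FAS and PP would have mixed causes.

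Most of this stands as a limit on the impact. The effect is confined to the supplementary estimand and the deviation outputs, it arises only if the row is applied as written, and the sizes above are illustrative. None of it makes row 13 agree with the protocol. Finalization before lock is an opportunity to correct the row, not evidence that it is right, and no other text in the SAP overrides it.

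**Conclusion.** The inconsistency is real and sits in current SAP text. As written, row 13 misclassifies validly enrolled participants with screening HBsAg above 5 and up to 100 IU/mL as major eligibility deviators and excludes them from the PP set without review. The FAS primary analysis is unaffected.

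The size rests on two assumptions, since the documents give neither figure. A share of 10% to 30% means about 10 to 31 of 102 participants wrongly excluded. A 20-point response difference on top of that means a PP-to-FAS shift of 2 to 6 points in either direction. The textual conflict depends on neither assumption.

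It should be corrected before lock. The study is open-label with sponsor-run interim analyses, and changing an analysis-set rule after results have been seen would be hard to defend.

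**What to change.** Replace the limit in both text columns of row 13 with the protocol's current criterion, A13.1 (screening HBsAg >5 IU/mL), and update the matching term in the issue system. Retain >100 IU/mL only for participants, if any, enrolled before Amendment 1 took effect at their site; the documents do not say whether there are any. Re-check any A13 deviations already logged.

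In the same edit, compare the whole of Table 13 with Amendment 1. Other rows also appear to predate it: row 7 (contraception reference), row 15 (HIV testing wording), row 32 (psychiatric wording in A24) and rows 45 and 46 (NA stopping, described without the completion criteria). There is also no row for the HBV DNA re-treatment criterion that the amendment added. These passages need to be reconciled; no view is taken here on the clinical rules themselves.

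For row 13 the cost is one table row and one deviation term. The wider check is a document comparison. Neither affects trial conduct, sample size or the primary analysis.

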Assessments and sampling include efficacy (eg, HBsAg, HBeAg, and HBV DNA), safety (eg, [S]AEs, labs, ECGs, vital signs, physical examinations), PK, PK/ PD, viral genome sequencing, PBMC, human leukocyte

^a Kim BK, Revill PA, Ahn SH, et al. HBV genotypes: relevance to natural history, pathogenesis and treatment of chronic hepatitis B. *Antiviral Therapy*. 2011;16:1169-1186

antigen (HLA) typing, immunogenicity and pharmacogenomic samples, blood sampling for exploratory analysis of host and viral markers, and medical resource utilization.

The total duration of individual participation will be up to 72 weeks (screening not included). Participants will be considered to have completed the study if they have completed all the assessments of the end of study (EOS) visit (ie, FU Week 48).

An internal Data Review Committee (DRC) will be commissioned for monitoring safety of participants enrolled in this study. In addition, an Independent Flare Expert Panel (IFLEP) will be appointed.

NA Re-treatment Criteria During Follow-up

Participants who meet the protocol-defined NA treatment completion criteria (based on the Week 24 or FU Week 2 results) will be monitored closely during the follow-up period with a study visit at least once every 4 weeks. They should re-start NA treatment immediately in the event of:

- Signs of decreasing liver function based on laboratory findings (eg, International Normalized Ratio [INR], direct bilirubin) or clinical assessment (eg, ascites, hepatic encephalopathy).
- HBV DNA value of >1,000,000 IU/mL (irrespective of confirmation and/or ALT increase).

Note: A post-treatment HBV DNA value of >100,000 IU/mL should trigger re-testing of ALT/AST, HBV DNA, and total and direct bilirubin within a maximum of 7 days from receipt of the data and further repeats as necessary (ie, weekly until HBV DNA returns to <100,000 IU/mL). A post-treatment HBV DNA value of >20,000 IU/mL (but <100,000 IU/mL) should trigger a re-test within 14 days. At all times, additional re-testing of the above parameters should be performed at the investigator's discretion.

In addition, re-start of NA treatment should be considered in the following cases:

- Confirmed post-treatment HBeAg seroreversion (HBeAg positive after it was negative at NA completion), OR
- Confirmed (at least 4 weeks apart) post-treatment increases in HBV DNA >2,000 IU/mL and ALT >5x upper limit of normal (ULN), OR

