6.5.1. NA Treatment Completion

All participants will receive the last dose of JNJ-3989 at Week 24 and the last dose of PegIFN- α 2a at Week 23 (Arms 1 and 2) or Week 11 (Arm 3). They will start the FU Period after the Week 24 visit. If all of the following NA treatment completion criteria are met based on the Week 24 results, treatment with NA will be stopped at the next scheduled visit (ie, FU Week 2):

- The participant has ALT <3x ULN, AND
- The participant has HBV DNA <60 IU/mL at Week 24 and HBV DNA <LLOQ at the previous visit, or HBV DNA <LLOQ at Week 24, AND
- The participant is HBeAg-negative, AND
- The participant has HBsAg <100 IU/mL.

Note: Participants who are close to meeting the protocol-defined NA treatment completion criteria with the Week 24 results, and do meet the criteria based on the FU Week 2 results may be allowed to stop NA at FU Week 4, after consultation with the Sponsor. In case of ALT elevation \geq 3x ULN at Week 24, the investigator must consider different potential causes of increased ALT to ensure appropriate work up and management as needed. If the ALT elevation is unrelated to HBV activity and/or <3x ULN by FU Week 2, NA completion may be considered at the discretion of the investigator and in consultation with the sponsor.

Participants who do not meet the above criteria based on the Week 24 or FU Week 2 results should continue NA treatment during the 48-week FU Period.

Participants who meet the above-mentioned NA treatment completion criteria will be monitored closely during the 48-week FU Period with a study visit at least once every 4 weeks. NA treatment should be re-started in accordance with the NA re-treatment criteria (see Section [6.5.2](#), NA Re-treatment Criteria During Follow-up, for more details).

The investigator should consider to re-start NA treatment per local standard of care at the EOS visit (Follow-up Week 48) for participants who met the NA treatment completion criteria based on the Week 24 (or FU Week 2) results, who did not re-start NA treatment during the follow-up phase, and who did not achieve and maintain HBsAg seroclearance. NA will not be provided by the sponsor after the final study visit.

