44	For PegIFN- $\alpha$ 2a, dose adjustment guidelines are recommended for participants who develop laboratory abnormalities during PegIFN- $\alpha$ 2a treatment, as recommended in the locally approved prescribing information for PegIFN- $\alpha$ 2a	Subject developed laboratory abnormalities but did not receive any PegIFN- $\alpha$ 2a dose adjustment  Recommended dose adjustments: -ANC <750 cells/mm  Reduce to 135 $\mu$ g -ANC <500 cells/mm  Discontinue treatment until ANC values return to more than 1,000 cells/mm  Reinstigate at 90 $\mu$ g and monitor ANC - Platelet <50,000 cells/mm  Reduce to 90 $\mu$ g - Platelet <25,000 cells/mm  Discontinue treatment	Received wrong treatment or incorrect dose	If classified as major protocol deviation (reviewed case by case), excluded from PP set	Yes
45	Subject stopped NA treatment at week 24, although some relevant changes in participant baseline status with regards to ALT, HBV DNA levels and/or HBeAg status were observed at Week 20 or any other event that in the opinion of the investigator could prevent stopping NA, were observed	Subject stopped NA treatment at week 24, although some relevant changes in participant baseline status with regards to ALT, HBV DNA levels and/or HBeAg status were observed at Week 20 or any other event that in the opinion of the investigator could prevent stopping NA, were observed	Received wrong treatment or incorrect dose	If classified as major protocol deviation (reviewed case by case), excluded	Yes

				from PP set	
46	Subject did not stop NA treatment at week 24, although no relevant changes in participant baseline status with regards to ALT, HBV DNA levels and/or HBeAg status or no other events that in the opinion of the investigator could prevent stopping NA treatment, were observed	Subject did not stop NA treatment at week 24, although no relevant changes in participant baseline status with regards to ALT, HBV DNA levels and/or HBeAg status or no other events that in the opinion of the investigator could prevent stopping NA treatment, were observed	Received wrong treatment or incorrect dose	If classified as major protocol deviation (reviewed case by case), excluded from PP set	Yes

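### SAP Table 13 rows 45-46 do not match the NA completion rule in protocol 6.5.1 and SAP 5.4.1.1.1, and no row names the HBV DNA >1,000,000 IU/mL re-start criterion

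*SAP*

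**What the plan says.** SAP section 1 fixes the protocol version: "This SAP is to be interpreted in conjunction with the clinical protocol amendment 1 finalized on 6 October 2021".

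Protocol 6.5.1 sets the completion rule: "If all of the following NA treatment completion criteria are met based on the Week 24 results, treatment with NA will be stopped". The stop falls at FU Week 2. FU Week 4 is possible, after sponsor consultation, for participants who narrowly miss on Week 24 results and meet the criteria at FU Week 2. The four criteria cover ALT, HBV DNA, HBeAg and HBsAg, the last worded as "The participant has HBsAg <100 IU/mL". Participants who do not meet them continue NA. SAP 5.4.1.1.1 repeats the four criteria.

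SAP Appendix 4, Table 13, uses other tests. Row 45 reads "Subject stopped NA treatment at week 24, although some relevant changes in participant baseline status with regards to ALT, HBV DNA levels and/or HBeAg status" and continues: "HBeAg status were observed at Week 20 or any other event that in the opinion of the investigator could prevent stopping NA". Row 46 is the mirror image: "Subject did not stop NA treatment at week 24, although no relevant changes in participant baseline status with regards to ALT, HBV DNA levels" or HBeAg, with a similar clause on other events in the investigator's opinion. Both rows are coded as wrong treatment or incorrect dose. Both have Intercurrent Event set to Yes, and per-protocol (PP) exclusion if the case is classified as major on individual review.

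For re-start, protocol 6.5.2 lists five criteria. Two call for immediate re-start, one of them HBV DNA above 1,000,000 IU/mL, "irrespective of confirmation and/or ALT increase".

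**The concern.** Two parts of the same SAP judge NA stopping by different visits and different parameters, and only one of them agrees with the protocol that the SAP names as its reference. Conduct that follows the protocol could be tabulated as wrong treatment, while some breaches would have no matching row.

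The flags also feed efficacy analyses. The PP set is defined by deviations that may affect the Week 24 primary endpoint, but the planned NA decision is taken at FU Week 2 or later, after the Week 24 sample. A flag raised there should not decide who counts in a Week 24 analysis.

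The missing re-start row matters for a separate reason. The amendment summary says that a re-start criterion was added so that significant HBV DNA increases are acted on irrespective of ALT, after a severe flare in another study.

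**Working it through.** The plan gives no figure to reproduce here, so the check sets the texts side by side.

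**Stopping rule**

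| Element | Protocol 6.5.1 (criteria repeated in SAP 5.4.1.1.1) | Table 13 rows 45-46 |
|---|---|---|
| When NA stops | FU Week 2, or FU Week 4 after consultation | Week 24 |
| Results used | Week 24, or FU Week 2 | Row 45: Week 20; row 46: none named |
| ALT | <3x ULN | relevant change from baseline status |
| HBV DNA | <60 IU/mL at Week 24 with <LLOQ at the visit before, or <LLOQ at Week 24 | relevant change |
| HBeAg | negative | relevant change |
| HBsAg | <100 IU/mL | not named |

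**Scenarios, with rows 45-46 read as written**

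- A. All four criteria met, no change from baseline, NA stopped at FU Week 2. This follows the protocol; row 46 flags it.
- B. No change in ALT, HBV DNA or HBeAg, HBsAg 100 IU/mL or more, NA continued. The protocol requires this; row 46 flags it.
- C. HBsAg 100 IU/mL or more, NA stopped at FU Week 2. A breach; row 45 does not name it. Row 46 might fire literally, but for the wrong reason.
- D. ALT, HBV DNA or HBeAg criterion first failed at Week 24, NA stopped at FU Week 2. A breach; row 45's Week 20 test misses it.
- E. All criteria met, no change, NA continued. A breach; row 46 catches it.

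**Re-start rule**

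Of the five criteria in protocol 6.5.2, Table 13 has rows for decreasing liver function (unnumbered), HBeAg seroreversion (47), HBV DNA >2,000 IU/mL with ALT >5x ULN (48) and HBV DNA >20,000 IU/mL (49). So 5 - 4 = 1 has no row: HBV DNA >1,000,000 IU/mL. Row 49 catches such a case only if HBV DNA stays above 20,000 IU/mL for at least 4 weeks, whereas the protocol criterion applies to a single unconfirmed value.

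**Where the flags reach**

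- Main estimator: SAP 5.3.2 makes a flagged participant a non-responder only if the endpoint is missing. SAP 5.3.2.1.4 already counts missing as non-response. No change.
- Sensitivity estimators 2 and 3: a participant still in the study, with Week 24 HBsAg missing and no intercurrent event, is left out (2) or takes a value within 4 weeks of Week 24 (3). With the flag, the same participant becomes a non-responder.
- PP supplementary estimand: exclusion, if the case is classified as major.

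**Direction in the PP set under scenario B**

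The fall in HBsAg is log10(baseline / Week 24). With baseline below 10,000 IU/mL and Week 24 at 100 IU/mL or more, it is less than log10(10,000/100) = 2, so the participant is a non-responder. Excluding such participants can only raise the PP response rate. As an illustration, assume 34 in an arm and 17 responders (the 50% planning rate). Excluding one non-responder moves 17/34 = 50.0% to 17/33 = 51.5%; excluding five gives 17/29 = 58.6%. The number actually excluded cannot be known from the documents.

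**The case against.** Several points on the other side stand.

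- Both documents describe follow-up endpoints as counted from completion of all interventions at Week 24, so Week 24 in row 46 may be shorthand that includes the FU Week 2 stop. That would remove scenario A. It does not remove B, C or D.
- The investigator-opinion clause in both rows, and row 66 for site-reported deviations not listed elsewhere, can absorb some gaps. That is partial cover: 6.5.1 makes HBsAg a fixed criterion, not a matter of opinion.
- Table 13 is by its own description a subset chosen for efficacy. SAP 5.4.2.1.2 summarises which completion criteria are unmet. SAP 5.4.2.1.3 summarises each re-treatment sub-criterion and cross-tabulates criteria met against actual re-start. So it would be wrong to infer that adherence is invisible. Neither section, however, sets meeting the completion criteria against actually stopping NA.
- PP exclusion is decided case by case, and the list is to be finalised before database lock.

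A reader might also infer more than the documents support. That re-start breaches in general go uncaptured is not so: four of five criteria have rows, and the one gap is separate from rows 45-46. That most of the 102 participants would be flagged rests on the most literal reading of Week 24 and ignores the case-by-case step. That the rows preserve a superseded rule is plausible: the amendment summary says completion criteria were added, and row 13 still has HBsAg >100 IU/mL against >5 IU/mL in inclusion criterion A13.1. But the pre-amendment protocol is not among the documents, so only the mismatch can be shown.

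**Conclusion.** The mismatch is real and can be checked from the texts alone. Rows 45-46 differ from protocol 6.5.1 and SAP 5.4.1.1.1 in visit, in the results used and in omitting HBsAg. As written they can flag conduct that the protocol requires and fail to name two kinds of stopping breach, although wrongful continuation is still caught. One of five re-start criteria has no row.

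The consequence is limited. The primary Week 24 result does not move, because missing data already count as non-response, and a reading that the primary analysis is compromised is not supported. What remains exposed is the PP supplementary estimand, the handling of missing values in sensitivity estimators 2 and 3, and the deviation tables. The size depends on how many cases are classified as major and how many Week 24 values are missing; neither is known. The point should be corrected, but it does not threaten the main conclusion. It takes no view on which NA stopping or re-start rule is clinically right.

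**What to change.** 1. Reconcile rows 45-46 with protocol 6.5.1 and SAP 5.4.1.1.1, so that all three use the same visits and the same four parameters.
2. Reconcile the re-start rows with protocol 6.5.2, so that every listed criterion, including HBV DNA >1,000,000 IU/mL, is represented in the deviation tabulation.
3. For NA decisions taken after the Week 24 sample, set both PP exclusion and Intercurrent Event to No for the Week 24 endpoint. If rows with No in both columns seem out of place in Table 13, carry them in the general tabulation of major deviations that Appendix 4 already plans for the FAS.

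The cost is edits to a few table rows and the matching deviation terms. Appendix 4 leaves the list open until database lock, so no data collection or primary analysis has to change.
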